6.3 PATIENT SETS ANALYSED

The following analysis sets will be defined for this trial:

- Screened set (SCR) All patients who signed informed consent; these patients will have completed routine procedures to establish the diagnosis of CVT.
- Treated set (TS): The set includes patients who received at least one dose of study medication.
- Full analysis set (FAS): This set includes all patients randomised.
- Per protocol set (PPS): This is a subset of the TS, restricted to patients without relevant important protocol violations as defined in Table 6.2: 1.

Proprietary confidential information © 2018 Boehringer Ingelheim International GmbH or one or more of its affiliated companies

The efficacy analysis (i.e. analysis of primary and secondary efficacy endpoints, as well as further endpoints based on the FAS will follow the intent-to-treat (ITT) principle. Patients will be allocated to the randomised treatment groups regardless of actual medication taken.

The safety analysis (including analysis of secondary safety endpoints

as well as adverse event analysis) will be based on the TS, and patients will be analyzed according to the treatment they have received.

Secondary efficacy analysis on the PPS may not be conducted if the number of patients excluded from the patient set is small (i.e. <10% of the TS).

Disposition data on the SCR will be presented according to the randomized treatment groups. For patients not entered/randomised on the total number will be presented.

			· · , ,	
		Pa	itient set	
Class of endpoint/data	SCR	TS	FAS	PPS
Primary endpoint (Section 5.1)			primary analysis	secondary analysis
Secondary and further efficacy endpoints (Section 5.2.2 and 5.3)			X	
Safety endpoints (Section 7.8)		Х		
Demographic/baseline data (Section 7.1)		Х	(X)	
Disposition	Х			

Table 6.3: 1Patient sets analyzed

(X) An additional FAS presentation of the demographic/baseline data may be provided in the End of Text section of the clinical trial report (CTR) if patient numbers for FAS and TS are clearly different, i.e. if $\geq 10\%$ of the TS are excluded from the FAS.

Note that the number of patients with available data for an endpoint may differ. For details, see Section 6.6 "Handling of missing data and outliers".

Proprietary confidential information © 2018 Boehringer Ingelheim International GmbH or one or more of its affiliated companies

Page 19 of 30

6.5 **POOLING OF CENTRES**

This section is not applicable because centre/country is not included in the statistical model.

6.6 HANDLING OF MISSING DATA AND OUTLIERS

A major goal of the trial is to obtain virtually complete follow-up of vital status and full collection of outcome event data. For the primary and secondary endpoints no general imputations are planned. In case of early discontinuation of patients with no follow-up and no events, those will be handled as imputed no event.

Missing or incomplete AE dates are imputed according to BI standards (see "Handling of missing and incomplete AE dates" [5]). The same philosophy will be applied to missing or incomplete outcome event and concomitant medication dates/times.

Other missing data will not be imputed.

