## **7.7 DETERMINATION OF SAMPLE SIZE**

It is planned to randomise 60 patients per arm, resulting in 120 patients randomised in total. Assuming a drop-out rate of 10%, this should result in 108 evaluable patients (54 per treatment arm).

Due to the rare nature of the disease (CVT incidence of around 2 per 100.000 per year), and with limited availability of patients in this indication, the planned sample size in this trial is not based on any statistical considerations. No hypotheses will be tested or confirmed.

Data about recurrence rates for CVT patients are limited; Martinelli et al. [[R15-5570](#)] report a 5% recurrence rate after discontinuation of anticoagulation within the first year. We assume a 2-3% event rate for the composite primary endpoint with 6 months of treatment.

The trial is designed as exploratory; a comparable frequency for the primary endpoint between dabigatran and warfarin would provide clinicians with important new information.

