6. GENERAL ANALYSIS DEFINITIONS

6.1 **TREATMENT(S)**

The following treatment periods based on actual start and stop dates/times of randomised study drug administration are defined:

- Screening: date of informed consent (time "0:00:00") to date of randomisation (time "0:01:00")
- Post-randomisation: date of randomisation (time "0:01:00") to time-point of first intake (date and time, "0:02:00" if time is missing) of randomised study drug.
- On-treatment: first intake (date and time)/date restarted of randomised study drug to date stopped/last intake (date and time) of randomised study drug. The residual effect period (REP) of 6 days will be added to this period.
- Off-treatment: date randomised study drug stopped + REP to date randomised study drug restarted
- Post-treatment: last intake (date/time) of randomised study drug + REP until date of trial completion. This is the date given on the termination page (trial completion page) of the eCRF. If date of trial completion is before last intake + REP, REP will be cut accordingly.
- Post-study: day after date of trial completion to database lock (DBL) + 1 day (time "0:00:00").

The REP is the time period after the last administration of trial medication when measurable drug levels or pharmacodynamic effects are still likely to be present. Events occurring in the REP are handled as occurring on-treatment. Data from the post-study period will only be listed.

For the analysis two observation periods are defined:

- Full observation period: from date of randomisation until the end of the trial, including all observed time on and off trial medication until the last known alive date (or date of death) This observation period will be used for the efficacy analysis.
- On-treatment: from date of first intake of trial medication until discontinuation of trial medication + REP

This observation period will be used for the safety analysis.

Despite the trial being open label, all activities conducted by the trial team will be performed in a blinded manner (as much as possible) until DBL. For example, data tabulations and listings will be presented using dummy treatment group information instead of actual treatment group allocations. The planned data review will be handled by the DMC in an unblinded manner (refer to the DMC SAP for more information).

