7. PLANNED ANALYSIS

Patient disposition (number of patients screened, randomised, treated, discontinued, etc...) will be presented for all patients.

Disposition as well as demographic and baseline data will be displayed by treatment group and overall. Primary, secondary and further as well as safety endpoints will be displayed by treatment group.

Descriptive statistics for continuous variables will generally be N (number of patients with non-missing values), mean, standard deviation (SD), minimum, Q1 (lower quartile), median, Q3 (upper quartile), maximum. In general, means, medians, Q1 and Q3 will be presented to one more decimal place than the raw data and SDs will be presented to two more decimal places. Minima and maxima will be presented to the same number of decimal places as the raw data.

Tabulations of frequencies for categorical data will include all possible categories and will display the number of observations in a category as well as the percentage relative to the respective treatment group. Percentages will be rounded to one decimal place. A missing category will be displayed if and only if there are actually missing values. Percentages will be based on all patients in the respective patient set whether they have non-missing values or not.

For calculations, 7 days will be considered 1 week, 30 days will be considered 1 month.

Generally, displays will follow [1], [3] and [6].

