7.4 PRIMARY ENDPOINT(S)

This is a prospective, randomised, open label, blinded endpoint (PROBE), active comparator trial and the clinical endpoints are being adjudicated by an AC in a blinded fashion. All analyses are exploratory, no statistical hypothesis will be tested.

The number and frequency of patients by treatment as well as by subgroup will be displayed along with the 95% confidence intervals (CIs). No difference between the treatments dabigatran etexilate versus warfarin will be tested.

Hazard ratios (HR) and 95% CI will be calculated as well; however the result will only be considered interpretable if the CI is not too wide, i.e. (lower limit of CI) \geq (estimate of HR / 4) and (upper limit of CI) \leq (4 * estimate of HR). A Cox proportional hazard model stratified by ICH at baseline will be applied.

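### Early discontinuers with no follow-up count as event-free but stay in the all-randomised denominator, so each arm's composite rate is biased slightly downward and no visible analysis checks it

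*SAP*

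**What the plan says.** SAP 6.6 plans no general imputation for the primary and secondary endpoints, with one exception: "In case of early discontinuation of patients with no follow-up and no events, those will be handled as imputed no event". Protocol 7.5 has the same sentence.

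The denominator follows from two further statements. SAP 6.3: "Full analysis set (FAS): This set includes all patients randomised". SAP 7: "Percentages will be based on all patients in the respective patient set whether they have non-missing values or not".

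The main display of the primary endpoint (SAP 7.4) is the number and percentage of patients with an event per arm, with a 95% confidence interval. The interval method is not named. A hazard ratio is added: "A Cox proportional hazard model stratified by ICH at baseline will be applied". The observation period for efficacy (SAP 6.1) runs from randomisation, "including all observed time on and off trial medication until the last known alive date (or date of death".

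SAP 6.6 also sets the goal of "virtually complete follow-up of vital status and full collection of outcome event data". Protocol 3.3.4.1 and 6.2.3 support that goal: patients who stop drug are followed to week 25 by contact and medical records unless they withdraw consent. The only missing-data sensitivity analysis in the visible text (protocol 7.5) concerns recanalisation.

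**The concern.** A patient whose VTE and bleeding status is unknown is recorded as having had neither. The rule can remove events from the count but cannot add any, so its error runs in one known direction.

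This trial tests no hypothesis, so the per-arm percentages and their intervals are its main result. Protocol 2.1 and 7.7 say that comparable percentages in the two arms would be informative to clinicians. With one or two events expected per arm, a single unobserved event would be visible in the result.

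The planned output also makes the rule hard to see. SAP 7 shows a missing category only when values are missing, and a patient recoded to no event is no longer missing. The reader would not know how many of the event-free patients were actually observed to week 24.

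**Working it through.** **Inputs.** 60 randomised per arm, 10% drop-out, and a planning assumption in protocol 7.7: "We assume a 2-3% event rate for the composite primary endpoint with 6 months of treatment". That is 60 × 0.02 = 1.2 to 60 × 0.03 = 1.8 events per arm. The number lost per arm (m), the time of loss and the risk in lost patients are not in the documents. They are assumptions here: m = 2, and m = 6 as an upper case in which every drop-out has unknown status.

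**1. The plan's own figure.** 120 × 0.90 = 108 and 60 × 0.90 = 54. The evaluable numbers in protocol 7.7 reproduce.

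**2. Bias when loss is unrelated to risk.** Use a constant hazard λ = −ln(1 − p)/168 per day. A lost patient has an observed event with probability q:

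- loss spread uniformly over 168 days: q = 1 − p/(168λ)
- loss at day 28: q = 1 − (1 − p)^(28/168)

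Reported rate = [(60 − m)p + mq]/60. Example with p = 2.5%, m = 6 and uniform loss: q = 1.255%, so (54 × 2.5 + 6 × 1.255)/60 = 2.376%.

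| True rate | 2 lost: uniform / day 28 | 6 lost: uniform / day 28 |
|---|---|---|
| 2.0% | 1.967 / 1.945% | 1.900 / 1.834% |
| 2.5% | 2.459 / 2.431% | 2.376 / 2.292% |
| 3.0% | 2.950 / 2.917% | 2.851 / 2.751% |

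The shortfall is 0.03-0.08 points with 2 lost and 0.10-0.25 points with 6 lost. If all 6 were lost at randomisation (q = 0), it would be 0.1p, or 0.2-0.3 points.

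**3. Upper 95% limit** (Clopper-Pearson assumed). Sample sizes of 59 and 57 approximate the information left when 2 or 6 are lost uniformly. Sizes of 58 and 54 apply if lost patients give none.

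| Events | As planned (n = 60) | 2 lost (n = 59 to 58) | 6 lost (n = 57 to 54) |
|---|---|---|---|
| 0 | 5.96% | 6.06-6.16% | 6.27-6.60% |
| 1 | 8.94% | 9.09-9.24% | 9.39-9.89% |

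**4. Chance of missing at least one event in an arm:** 1 − [1 − (p − q)]^m. Under uniform loss it is 2-3% with 2 lost and about 6-9% with 6 lost. Loss at day 28 raises this to about 3-5% and 10-14%. One missed event is the difference between 1/60 (1.7%) and 2/60 (3.3%).

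**5. Loss related to risk or to arm.** If 10% are lost at the start with three times the risk of the others, the shortfall is 0.10 × 3p = 0.6-0.9 points. If 5% are lost in one arm and 15% in the other at equal risk, the between-arm difference shifts by 0.10p = 0.2-0.3 points. As an outer bound, counting all 6 lost patients as events takes 1/60 to 7/60 (11.7%, interval 4.8-22.6%).

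**6. Can the hazard ratio act as the check?** SAP 7.4 calls it interpretable only if the limits lie within a factor of 4 of the estimate, approximately exp(1.96√(1/d1 + 1/d2)) ≤ 4 for d1 and d2 events. Three events per arm give 4.95, and four per arm just meet it (3.998). So about 8 events are needed, against 2.4-3.6 expected in total. The chance of 8 or more in 120 is 0.3% at 2% and 2.9% at 3%.

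**7. Would restricting to known status be better?** With p = 2.5% and 6 lost uniformly, patients with an event before loss stay in and the other lost patients drop out. Expected events are 54 × 0.025 + 6 × 0.01255 = 1.425, and the expected denominator is 54 + 6 × 0.01255 = 54.08. The ratio is 2.64%, an error of +0.14 points against −0.12 for the plan.

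**The case against.** The strongest reply is that this is negligible. A shift of at most about a quarter of a point sits inside an interval 9-11 points wide. There is no margin or decision rule to cross, and the same rule applies to both arms, so equal loss leaves the comparison almost unchanged. Follow-up after stopping drug is well designed. Patients are asked to report at least the primary endpoint events, and those who refuse contact are asked to name someone else who may be contacted. All of this stands, and it sets the severity low. It does not remove the bias or show how many patients were affected.

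Four stronger readings are tempting, but the documents do not support them:

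- *That disposition tables will show only who stopped drug.* Protocol 3.3.4.1 separates stopping drug from leaving the study, protocol 8.3.1 records each with its own date, and SAP 6.1 uses the trial-completion date. A close proxy for unknown status can be derived. It is just not planned as a display for the composite.
- *That protocol 7.7 contradicts the SAP by calling only 54 per arm evaluable.* It does not define drop-out as loss of outcome, and it says that the sample size has no statistical basis.
- *That the Cox model will keep patients known only to be alive at risk as event-free.* SAP 6.1 ends the efficacy observation period at the last known alive date, and SAP 6.6 names vital status and outcome events separately, so this is possible. No visible text gives the Cox censoring rule.
- *That no check exists at all.* SAP sections 5.3, 6.4 and 7.6 are not in the public text, so the statement is limited to what is visible.

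**Conclusion.** The point holds as a low-severity improvement. The imputation rule together with the all-randomised denominator can bias each arm's composite rate and upper limit only downward. Under loss unrelated to risk and a true rate of 2-3%, the size is 0.03-0.08 points with 2 lost per arm and 0.10-0.25 points with 6 lost. The second range treats the whole planned drop-out as outcome-unknown, which the planned follow-up makes unlikely. Both ranges assume a constant hazard and loss between day 28 and uniform over the 24 weeks.

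A reader might infer that the rule distorts the comparison between arms or undermines the trial's conclusion. The documents do not support that: they give no reason to expect unequal or risk-related loss, and no formal conclusion depends on the figure. The gap is that, if such loss did occur, the planned output would not show it.

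**What to change.** In SAP 6.6 and 7.4:

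1. Keep the crude count and percentage on all randomised patients as planned.
2. Report per arm the number of patients whose VTE/bleeding status to week 24 is incomplete. This can be derived from trial-completion dates and from the visits or contacts at which these events were asked about.
3. Add a Kaplan-Meier 24-week risk per arm with a 95% interval. Censor it at the last contact at which VTE/bleeding status was obtained, not at the last known alive date, and use the same censoring for the Cox model. State how a death without an event is treated.
4. Add a best/worst-case or tipping-point row, because Kaplan-Meier does not address loss that is related to risk.
5. Do not replace the estimate with an exact interval on known-status patients only, since that is biased upward (working, step 7). If an arm has no events, show the exact interval on all randomised patients next to the unknown-status count. The chance of no events in an arm, (1 − p)^60, is 30% at 2% and 16% at 3%.

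The cost is SAP wording, one or two extra tables and slightly wider intervals. No trial procedure changes. The flow chart already schedules bleeding and VTE collection at Visits 2 to 7, so the date of the last visit or contact can be used if no separate status date is recorded.

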6.7 BASELINE, TIME WINDOWS AND CALCULATED VISITS

The baseline assessment is the last measurement made (or sample taken) prior to first study drug administration. The first study drug administration should occur at Visit 2. Any assessments made on this day, where time is not collected, are assumed to be prior to study

Proprietary confidential information © 2018 Boehringer Ingelheim International GmbH or one or more of its affiliated companies

drug administration. This does not apply to adverse events (AEs) and outcome events where it will be assumed that events occurred on-treatment.

Actual dates will be used for assigning AEs and outcome events to the appropriate treatment period as defined in Section 6.1. Windowing with regard to visits will not be applied as the main objective of this trial is the collection of outcome events, which are not necessarily associated with clinic visits.

7. PLANNED ANALYSIS

Patient disposition (number of patients screened, randomised, treated, discontinued, etc...) will be presented for all patients.

Disposition as well as demographic and baseline data will be displayed by treatment group and overall. Primary, secondary and further as well as safety endpoints will be displayed by treatment group.

Descriptive statistics for continuous variables will generally be N (number of patients with non-missing values), mean, standard deviation (SD), minimum, Q1 (lower quartile), median, Q3 (upper quartile), maximum. In general, means, medians, Q1 and Q3 will be presented to one more decimal place than the raw data and SDs will be presented to two more decimal places. Minima and maxima will be presented to the same number of decimal places as the raw data.

Tabulations of frequencies for categorical data will include all possible categories and will display the number of observations in a category as well as the percentage relative to the respective treatment group. Percentages will be rounded to one decimal place. A missing category will be displayed if and only if there are actually missing values. Percentages will be based on all patients in the respective patient set whether they have non-missing values or not.

For calculations, 7 days will be considered 1 week, 30 days will be considered 1 month.

Generally, displays will follow [1], [3] and [6].

7.1 DEMOGRAPHIC AND OTHER BASELINE CHARACTERISTICS

Only descriptive statistics are planned for this section of the report. Data from the demographic, as well as medical and surgical history eCRF pages will be presented, including details on CVT history.

With regard to demographic data the following categorisations will be considered, in addition to the continuous data:

- Age class (years): $<30, \ge 30 <40, \ge 40 <50, \ge 50 <60, \ge 60 <70, \ge 70 <80, \ge 80$
- Weight class (kg): $<30, \ge 30 <60, \ge 60 <90, \ge 90$
- Body mass index (BMI) class (kg/m^2) : < 18.5, $\ge 18.5 <25$, $\ge 25 <30$, ≥ 30

The National Institutes of Health Stroke Scale (NIHSS) will be recorded, if it had been collected at the time of qualifying (index) CVT. In patients, where NIHSS has not been done at the time of index CVT, it will be performed at study entry (at Visit 1). It is a tool used by healthcare providers to objectively quantify the impairment caused by a stroke. The NIHSS is composed of 11 items, and for each item a score of 0 typically indicates normal function in that specific ability, while a higher score is indicative of some level of impairment. The individual scores from each item are summed in order to calculate a patient's total NIHSS score. The maximum possible score is 42, with the minimum score being a 0 ([16], [17]).

Page 22 of 30

Proprietary confidential information © 2018 Boehringer Ingelheim International GmbH or one or more of its affiliated companies

Table 7.1: 1	NIHSS score
--------------	-------------

Score	Stroke Severity
0	No Stroke Symptoms
1-4	Minor Stroke
5-15	Moderate Stroke
16-20	Moderate to Severe Stroke
21-42	Severe Stroke

7.2 CONCOMITANT DISEASES AND MEDICATION

Only descriptive statistics are planned for this section of the report.

Baseline conditions will be coded according to the most recent version of the Medical Dictionary for Regulatory Activities (MedDRA), and summarized by ATC class 3 and preferred name (PN). The frequency of patients with different baseline conditions will be presented.

Therapies will be classified using the most recent version of the World Health Organisation – Drug Dictionary (WHO-DD), and the frequency of patients with therapies will be presented according to whether these were concomitantly taken during the on-treatment period defined in Section 6.1, or whether these are prior or post therapy.

Details on administration of commercially available idarucizumab – including indication, information on surgery / invasive procedures and bleeding – will additionally be listed.

7.3 TREATMENT COMPLIANCE

Cumulative days of temporary treatment interruptions will be summarized in classes $(0, 1 - <5, 5 - <10, 10 - <20, 20 - <30, \ge 30)$. Frequency of patients with treatment interruptions for AEs as well as for other reasons will be presented. Additionally, time to first temporary treatment interruption will be analyzed. For this purpose, patients who permanently discontinue from treatment before having had a temporary treatment interruption will be censored at time of treatment discontinuation.

Treatment compliance will be calculated as follows:

7.3.1 Dabigatran Compliance

Based on capsule counts, treatment compliance (%) will be calculated as:

Dabigatran compliance (%) = $\frac{\text{Number of tablets actually taken } \times 100}{\text{Number of tablets which should have been taken}}$

This value will be entered directly into the eCRF.

Only treatment interruptions not due to AE will be considered as a compliance issue and will be taken into account in the calculation (duration of interruptions due to AE will be subtracted from the duration of the study period).

Dabigatran compliance will be summarised continuously and in classes (<80%; 80-120%; >120%).

A patient will be considered as non-compliant if the number of doses taken is not between 80-120% of the expected number of doses.

